#### 5.8.1.1 Subsets

- Non-serious adverse events will be presented by dose level (part A) or treatment group (parts B), system organ class and preferred term

- Related (BGB324) adverse events will be presented by dose level or treatment group, system organ class and preferred term.
- Related (Cytarabine) adverse events will be presented by system organ class and preferred term. (Part B2 only)
- Related (Decitabine) adverse events will be presented by system organ class and preferred term. (Part B3 only)
- Related (Other Anti-Cancer Medications) adverse events will be presented by dose level or treatment group, system organ class and preferred term.
- Serious adverse events will be presented by dose level or treatment group, system organ class and preferred term
- Related (BGB324) serious adverse events will be presented by dose level or treatment group, system organ class and preferred term.
  - Related (Cytarabine) serious adverse events will be presented by system organ class and preferred term. (Part B2 only)
  - Related (Decitabine) serious adverse events will be presented by system organ class and preferred term. (Part B3 only)
  - Related (Other Anti-Cancer Medications) serious adverse events will be presented by dose level or treatment group, system organ class and preferred term.
  - Serious adverse events will be presented by dose level or treatment group, system organ class, preferred term, and maximum CTCAE grade.
- Adverse events leading to discontinuation will be presented by dose level or treatment group, system organ class and preferred term.
- Adverse events  $\geq$  Grade 3 will be presented by dose level or treatment group, system organ class and preferred term.
  - Related (BGB324) adverse events  $\geq$  Grade 3 will be presented by dose level or treatment group, system organ class and preferred term.
  - Related (Cytarabine) adverse events  $\geq$  Grade 3 will be presented by system organ class and preferred term. (Part B2 only)
  - Related (Decitabine) adverse events  $\geq$  Grade 3 will be presented by system organ class and preferred term. (Part B3 only)
- The most frequent MedDRA preferred terms ( $\geq 10\%$  subjects in the overall safety population restricted to each part) will be presented by dose level or treatment group.
- Separate listings will be produced for DLTs, SAEs, related (all 3 types) AEs, discontinuations due to AEs, and events of  $\geq$  Grade 3 severity.
- A listing of death occurring during the study with time interval between first/last intake date and death date, as well as a flag for only Early Death during the first 4-week period after C1D1 will also be presented.

All other information collected (e.g. action taken) will be listed as appropriate.

**Notes:**

- AEs coded using MedDRA version 17.0 or higher

### **5.8.2 Physical Examination**

Any new or worsened post-baseline physical examination findings during the safety evaluation period will be recorded as AEs and summarized in terms of AEs as described in Section 5.8.1. Both the complete physical examination performed at screening and the symptom directed physical examination results will be presented in data listings.

### **5.8.3 Vital Signs**

Results for weight (kg), systolic and diastolic blood pressure (mmHg), pulse rate (BPM), respiration rate (BREATHS/MIN), and temperature (°C) will be summarised by dose cohort and scheduled visit, as well as Change from Baseline. Height (cm) at screening will be summarized with the demographics, but presented with other vital signs in the listing.

### **5.8.4 Eastern Cooperative Oncology Group**

ECOG performance status will be summarized categorically at each scheduled visit with frequencies and percentage.

### **5.8.5 Electrocardiograms**

The quantitative ECG assessments (PR interval, RR interval, QRS Duration, QT interval, and QTcF interval) will be summarised for actual values and Change from Baseline to each visit/timepoint will be also presented.

ECG overall interpretation (normal, abnormal not clinically significant and abnormal clinically significant) will be presented as a categorical summary by dose cohort and scheduled visit.

### **5.8.6 Echocardiograms**

Any new or worsened post-baseline echocardiogram findings during the safety evaluation period will be recorded as AEs and summarized in terms of AEs as described in Section 5.8.1. All echocardiogram results will be presented in a data listing.

### **5.8.7 Laboratory findings**

Results from the following laboratory parameters, recorded at scheduled visits, will be presented in listings:

#### **Hematology:**

Hemoglobin, Hematocrit, Red Blood Cells (RBC), Mean Corpuscular Hemoglobin (MCH), Mean Corpuscular Hemoglobin Concentration (MCHC), White Blood Cells (WBC), Neutrophils, Eosinophils, Basophils, Lymphocytes, Monocytes, Platelets, and Blasts (in percent).

#### **Clinical Chemistry:**

Sodium, Potassium, Calcium, Chloride, Magnesium, Inorganic Phosphate, Creatine phosphokinase, Serum Creatinine, CK-Myocardial B, Total Protein, Total Bilirubin, Direct Bilirubin, Indirect Bilirubin, Albumin, Alkaline Phosphatase (ALP), Alanine Aminotransferase (ALT), Aspartate Aminotransferase (AST), Glucose, Uric Acid, and Blood Urea Nitrogen (BUN).

**Urine:**

pH, Specific Gravity; semi-quantitative "dipstick" evaluation of Proteins, Glucose, Ketones, Blood, Bilirubin, Nitrite, Leukocytes, and Urobilinogen, and a microscopic examination including Casts, Crystals, RBC, and WBC.

**Coagulation:**

Prothrombin Time (PT), Activated Partial Thromboplastin Time (APTT), International Normalized Ratio (INR), and Quick Test.

Numeric Hematology and Clinical Chemistry parameters will be summarised along with each corresponding Change from Baseline for all scheduled visit by dose level or treatment group. The incidence of laboratory test results outside the normal range will be listed by dose cohort and time point.

The following shift tables from baseline to all the cycles of hematology CTCAE grades will also be displayed by dose level or treatment group:

- All post baseline grades according to all baseline grades
- Number of patients with at least CTCAE Grade 2 according to all baseline grades

Finally, number of patients with at least CTCAE Grade 3 at each visit will be summarized.

Clinically significant treatment-emergent laboratory findings will be summarised as adverse events.

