7.1.2. Summary of Pre-clinical Toxicology

To support clinical studies with bemcentinib a series of animal toxicology and safety studies, including 28-day repeat dosing studies in rodents and monkeys and a single dose telemetered cardiovascular (CV) safety study in monkeys, have been conducted. Comparisons of the data reported in the rodent and monkey studies indicate that primates are more sensitive to bemcentinib on a per body weight basis.

The results of the repeat dose 28-day study in monkeys identified the liver, reticuloendothelial system and hematopoietic system as target organs. These events were largely thought to be due to macrophage accumulation, consistent with phospholipidosis, and were only partially reversible across the planned 16-day recovery period, although this was anticipated to be due to the slow elimination of the compound. Similar findings were identified in mice treated across a range of dose levels with partial recovery noted 16 days later.

In the CV safety study, single oral administration of bemcentinib (7.5 mg/kg – 60 mg/kg) was associated with recoverable, non-adverse decreases in heart rate and corresponding increases in the RR interval durations. Dose-dependent increase in QTc interval was noted at all dose levels; the magnitude of the QTc effect at the highest dose level was 17%, whilst at 7.5 mg/kg and 15 mg/kg, the change generally fell below 10% compared to vehicle control

and pre-dose values. These observations were consistent with the previously identified IC₅₀ for human ether-à-go-go related gene (hERG) channel inhibition of 0.53 µM bemcentinib.

Bemcentinib was negative in the Ames bacterial mutation assay, suggesting that bemcentinib is not mutagenic. Bemcentinib was also negative in an *in vitro* mammalian cell cytogenetic study in human lymphocytes suggesting that bemcentinib is not clastogenic.

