13.2. Laboratory Safety Assessments

Blood and urine samples will be taken at times specified in the relevant Schedule of Events (Tables 4-6) in Section 11, and at any other time required in the opinion of the investigator, and analyzed at the designated local laboratory.

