16.4.2. Methods of Analysis

No formal statistical analysis will be performed. AEs will be coded using the Medical Dictionary for Regulatory Activities (MedDRA) Version 15.0 or above. The number and percentage of patients reporting treatment-emergent AEs will be tabulated by preferred term and system organ class and summarized by both CTCAE grade and relationship to study drug. All AEs commencing prior to dosing with study medication will be excluded from the tabulation but will be fully listed. AEs that have missing onset dates will be considered to be treatment-emergent, unless the stop date is known to be prior to the first administration of bemcentinib.

Separate listings will be produced for DLTs, SAEs, discontinuations due to related AEs, and events of ≥Grade 3 severity.

Summary statistics by dose cohort and time point will be produced for vital signs, ECG parameters and laboratory safety data, together with changes from baseline. The incidence of laboratory test results outside the normal range will be summarized by dose cohort and time point. Laboratory test results outside the normal range will be individually listed for clinical review. Abnormal ECG results will be summarized by dose cohort.

Changes in PR, QT interval and QTcF duration will be analyzed according to administered dose and ultimately modelled with corresponding plasma concentrations of bemcentinib when available.

Any patient treated with bemcentinib beyond disease progression will be followed for the same safety and efficacy assessments as for all other patients enrolled into the study. The data for patients treated beyond progression will be presented in both a combined output (with all patients) and also a separate output (reflecting a new period of analysis with the data collected in this period). All data collected will be included in the study CSR and may be presented at congress/symposia.

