## 5.14 Changes in Conduct or Planned Analyses from the Protocol

Following are the changes in analyses from those defined in the protocol:

- Population of analysis is updated to match with the usual definition in clinical trials. In the protocol, safety population and efficacy population have the same definition and per protocol population definition is the typically definition of efficacy population. Then, the efficacy population is updated with definition of per protocol and it is decided that no per protocol analysis will be handled.
- The exploratory objective "To explore the correlation between baseline biomarker levels and clinical endpoints". Biomarker data will be analyzed in exploratory analyses not in scope of this SAP so this analysis will be presented within biomarker analysis.

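### The SAP turns the protocol's summary of out-of-range laboratory results into a listing without declaring it, and limits shift tables to hematology, so liver test rises below Grade 3 reach no laboratory incidence or shift table

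*SAP*

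**What the plan says.** Protocol 16.4.2 (safety, methods of analysis) sets two requirements. The first is a summary: "The incidence of laboratory test results outside the normal range will be summarized by dose cohort and time point". The second is a listing: "Laboratory test results outside the normal range will be individually listed for clinical review".

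SAP 5.8.7, in the text after the coagulation parameters, says: "The incidence of laboratory test results outside the normal range will be listed by dose cohort and time point". It then plans grade-shift tables for one panel: "The following shift tables from baseline to all the cycles of hematology CTCAE grades will also be displayed". It adds a count of patients at Grade 3 or above at each visit, and says that clinically significant treatment-emergent findings will be summarised as adverse events. Repeat and unscheduled results are listed only.

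SAP 5.14 opens with "Following are the changes in analyses from those defined in the protocol" and gives two items: the analysis populations and the biomarker correlation. Neither concerns laboratory data.

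On why liver tests matter here, Protocol 7.1.2 says: "The results of the repeat dose 28-day study in monkeys identified the liver, reticuloendothelial system and hematopoietic system as target organs". Protocol 13.2 has samples "analyzed at the designated local laboratory", and Protocol 9.1 expects about 20 sites.

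**The concern.** Safety and tolerability is the primary objective of Part B, and clinical chemistry is one of the safety endpoints in Protocol 8.2.1. The out-of-range incidence summary is the laboratory output that counts abnormal values whatever their grade and without any judgement of significance or causality. The SAP drops it. The hematopoietic system still has its own shift tables, but the liver tests have none.

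What remains for mild and moderate liver test rises is either a group-level statistic or a count that depends on the investigator reporting an adverse event. A reader of the study report could not say from a laboratory table how many patients in a cohort had ALT, AST, ALP or bilirubin above normal, or how many had worsened from baseline, unless the rise reached Grade 3.

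**Working it through.** No formula in the plan is at issue. The check sets the passages and the table list side by side.

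1. **Wording.** The sentences in Protocol 16.4.2 and SAP 5.8.7 match except for one verb: summarized in the protocol, listed in the SAP. The protocol's next sentence already asks for a listing, so the listing was meant to accompany the summary and not to replace it.

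2. **Table list.** SAP 6.3.3.2 holds 14 laboratory tables:
   - hematology summary and change from baseline: 2 (14.3.5.1.1.x)
   - hematology grade shifts: 4 (14.3.5.1.2.x and 14.3.5.1.3.x)
   - Grade 3 or above: 4 (14.3.5.1.4.x and 14.3.5.4.1.x)
   - coagulation summary and change: 2 (14.3.5.2.1.x)
   - chemistry summary and change: 2 (14.3.5.3.1.x)

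   2 + 4 + 4 + 2 + 2 = 14. Out-of-range incidence tables: 0. Chemistry shift tables: 0. The list therefore agrees with the altered verb.

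3. **Declaration.** Of the two changes declared in SAP 5.14, none is about laboratory results.

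4. **Where a liver test rise below Grade 3 can appear.** The Grade 3 tables are read generously here, as covering chemistry, because their titles do not limit them to hematology.
   - Chemistry summary tables: SAP 5.1 gives n, mean, SD, median, minimum and maximum. These show an extreme value but do not count patients.
   - Adverse event tables by preferred term and CTCAE grade (14.3.1.2.2.x): the rise is counted at any grade, if it was reported as an event.
   - Listings: the chemistry listing with out-of-range flags (16.2.8.3) and the listing of clinically significant results (16.2.8.5).

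5. **Limits of the adverse event route.** Protocol 15.1.1 offers its criteria for clinical significance as suggestions. Under Protocol 9.3.4 and 15.2.1, only treatment-related events need be recorded between the last bemcentinib dose and the end of the 28-day follow-up, yet Protocol 11.4 still takes a chemistry sample at the Final Study Visit. An abnormal value at that visit that is judged unrelated need not become an adverse event.

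6. **Illustration (assumed values).** Take 14 patients in a cohort, one rising by 3 units and 13 unchanged. The mean change is 3/14 = 0.21 and the median change is 0. The maximum change is 3, so the value is visible, but the table does not say how many patients were above normal or what their baseline status was.

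**The case against.** The strongest reply is that the data are not hidden. Rises judged clinically significant enter adverse event tables that have no Grade 3 floor, and the suggested criteria are broad: closer follow-up, further investigation, or a change in study drug or concomitant treatment each suffices. The chemistry summaries show the maximum. Out-of-range values are flagged and listed, and with up to 14 or 20 evaluable patients per Part B cohort a reviewer can read the listings patient by patient. An IDMC monitors safety. All of this stands. A reader might infer that liver test rises below Grade 3 reach no incidence table at all, or that the report could show no hepatic signal when one exists. The documents support neither.

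The liver premise is also limited. It comes from one monkey study that names three target organs or systems, attributes the findings largely to macrophage accumulation consistent with phospholipidosis, and puts the partial recovery down to slow elimination. Table 2 of the protocol lists no hepatic event in healthy volunteers. This lowers the urgency but does not account for the missing summary, which the protocol requires for all laboratory tests.

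Chemistry shift tables were never promised in the protocol, so adding them is a recommendation and not a correction. The altered verb may be a drafting slip. That is possible, but the table list has no such table either.

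Finally, the SAP covers four country protocols and cites US version 9.0, whereas the protocol supplied is US version 10.0. The version 9.0 wording and the separate shells file cannot be checked.

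**Conclusion.** The point holds as a reporting gap. Measured against the supplied protocol, one promised safety output is missing from both the SAP text and its table list, and the change is not declared. Liver tests have 0 shift tables against 4 for hematology. Rises in ALT, AST, ALP or bilirubin below Grade 3 reach no laboratory incidence or shift table and are counted only through adverse event reporting.

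How many patients this would affect cannot be estimated from the documents. The conclusion rests on two assumptions: that the table list in SAP 6.3.3.2 is complete, and that the summary requirement in version 10.0 applies to the final analysis.

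A reader might also take the liver limits in exclusion criterion 8 as a ready-made definition of hepatic injury. They are not one. They are entry limits joined by *or*, they allow a higher transaminase limit (5 x ULN) when leukemia involves the liver, and they say nothing about change from baseline.

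**What to change.** In SAP 5.8.7, restore the protocol's verb so that out-of-range incidence is summarized by dose cohort and time point, and keep the listing. Add the matching tables for Part A and Part B to section 6.3.3.2.

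Extend the CTCAE grade-shift tables to ALT, AST, ALP and bilirubin, by cohort, from baseline to worst post-baseline grade, graded against each local laboratory's normal range. State whether unscheduled and repeat results count towards the worst grade, since they are now listed only.

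If the summary was dropped deliberately, declare and justify that in SAP 5.14 instead.

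A table pairing transaminase and bilirubin rises is optional. If added, it should be descriptive, show baseline status, and not be presented as a definition taken from exclusion criterion 8.

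The cost is SAP wording and a few descriptive tables: two for out-of-range incidence and two for liver shifts if one of each is made per part. Normal-range flags are already planned for the listings, so no new samples or visits are needed.

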**Notes:**

- All results outside predefined normal ranges will be flagged in the data listings.
- Repeat laboratory results within a visit will not be used in any summary calculations. Unscheduled and repeat results will be listed only
- Serum Pregnancy Test results will be listed.
- Any other laboratory results will be listed only.

## 5.9 Pharmacokinetic Analysis

The Pharmacokinetic Analysis will be conducted separate from this analysis. Details will be found in a specific analysis plan.

## 5.10 Pharmacodynamic Analysis

The Pharmacodynamic Analysis will be conducted separate from this analysis. Details will be found in a specific analysis plan.

## 5.11 Protocol Deviations

Deviations from the protocol will be documented on an ongoing basis by the study monitors and project manager throughout the study period.

At the time of database lock, while the protocol deviations are being reviewed, the project manager will forward all relevant documentation highlighting protocol deviations to the study

statistician. These deviations will be included in the protocol violation document for agreement and will be listed with the protocol violations in the CSR.

## 5.12 Missing Values – Missing Visits

Missing, unused and spurious data will be considered missing at random and dealt with as such. There is no intention to implement any procedure for replacing missing data.

In case of missing or partially missing dates for initial diagnosis, the following rules will be applied:

- If initial diagnosis date=../mmm/yyyy (= missing day), then it will be substituted by **01/mmm/yyyy**
- If initial diagnosis date=.../.../yyyy (= missing day and month), then it will be substituted by **01/JAN/yyyy**
- If initial diagnosis date=.../.../.... (= completely missing), then it won't be substituted.

## 5.13 Deviations from SAP

Any deviations from the statistical plan will be described and justified in the final clinical study report.

## 5.14 Changes in Conduct or Planned Analyses from the Protocol

Following are the changes in analyses from those defined in the protocol:

- Population of analysis is updated to match with the usual definition in clinical trials. In the protocol, safety population and efficacy population have the same definition and per protocol population definition is the typically definition of efficacy population. Then, the efficacy population is updated with definition of per protocol and it is decided that no per protocol analysis will be handled.
- The exploratory objective "To explore the correlation between baseline biomarker levels and clinical endpoints". Biomarker data will be analyzed in exploratory analyses not in scope of this SAP so this analysis will be presented within biomarker analysis.

## 5.15 Algorithms/SAS Codes

- **Tables that need 95% CIs within group for binomial proportions:**

```
PROC FREQ DATA=dset;  
  BY byvar; (optional)  
  TABLES var1/binomial (exact p=.05 alpha=0.05);  
  EXACT BINOMIAL;  
RUN;
```

- **Tables that need life table with estimates of survival, with CIs:**

```
PROC LIFETEST DATA=dset OUTSURV=LIFE METHOD=KM;  
  BY treatment;  
  TIME duration*censor (0 or 1);  
RUN;
```

# 6 Tables and Listings

## 6.1 Table Format

All output will be produced using SAS version 9.2 or a later version.

In the top left portion of each table/listing, a *table/listing number* followed by the *title* of the table/listing will be presented. After the title line, optional *sub-title* or *population* information can be presented. Horizontal lines will appear before and after the column heading of the table/listing. *Footnotes* will be put under the main body of text at the bottom of the page.

The *sponsor name*, *protocol number*, programmers User ID, status of the table/listing (i.e. draft or final) and *SAS program name* will appear bottom left in a string and the *page number* will appear on the bottom right corner of each table/listing. The *date and time of creation* of table/listing will appear bottom left under the sponsor name. The source listing number will appear bottom left.

A *landscape layout* is proposed for both table and listing presentations.

The *left and right margins* of all tables and listings will be a minimum of 2.1 cm from the left and 1.9cm from the right. The *top and bottom margins* will be a minimum 2.92cm. *Header and footer* will be both 1.27 cm.

There is no special requirement of *font type* and *size*, but an *8-point* font size for tables and *7-point* for listings is proposed using *Courier New* font. A maximum SAS line size=141 and page size=44 for *8-point* font size, and line size=161 and page size=50 for *7-point* will be used so as to fit on both UK and US paper sizes.

In a listing, in the case that a subject's record has been continued to the next page, an appropriate identification (e.g., the subject ID number) must be presented at the beginning of that page.

